Study protocol - for registration in ClinicalTrials.gov

Effect of COVID-19 lockdown on alcohol and tobacco use in two Chilean universities: a difference-in-difference analysis

Sponsor: Universidad de La Frontera

Organisation's unique protocol ID: ANID - COVID0282

Principal investigators:

[name], Universidad de La Frontera, Temuco, Chile [name], Universidad Católica del Norte, Coquimbo, Chile

Collaborators:

[name], PhD, Finnish Institute for Health and Welfare, Helsinki, Finland [name], Universidad de La Frontera, Temuco, Chile [name], Universidad de La Frontera, Temuco, Chile

Version: 1.0

Version date: October 5, 2021

Effect of COVID-19 lockdown on alcohol use in two Chilean universities: a difference in-difference analysis

Background

The coronavirus disease 2019 (COVID-19) pandemic has led to substantial societal changes in most high and middle-income countries. This can translate to changes in the volume and patterns of alcohol use, with severe consequences for health and societal wellbeing [1].

The COVID-19 pandemic could potentially affect alcohol and tobacco use in several ways. First, governments have introduced policies to reduce viral transmission, including social distancing policies to restrict people's mobility and exposure to SARS-CoV-2. These have ranged from stay-at-home advice and remote-work guidance to statutory closures of schools and universities, bars and restaurants and restrictions for public gatherings [2, 3]. The most restrictive policies have included lockdowns (with various levels of stringency) and curfews. Such policies have disrupted routines and reshaped social interactions as well as acting as an acute stressful event, which could, in turn, affect alcohol and tobacco use [1, 4-6].

Second, the pandemic could directly impact alcohol and tobacco use through changes in affordability due to the negative economic consequences, reducing people's disposable income and consumption as a result [7]. A SARS-CoV-2 infection could also directly impact tobacco or alcohol use, as the majority of infected individuals have experienced fever, malaise or cough [8]. An estimated 10% of those who had COVID-19 persist with fatigue, dyspnoea, disturbance of smell or taste after 8-24 weeks, which could affect their alcohol use [9]. Persistent COVID-19 symptoms have been reported to be as high as 50% among those who were hospitalized due to COVID-19 [10].

Third, governments have adopted policies that directly influence alcohol and tobacco availability and affordability. Such policies include total ban of tobacco (South Africa)[11] or alcohol sales (e.g. South Africa, India, Thailand, Panama),[12-15] changes in opening hours (as in parts of Chile and Mexico) and even raised alcohol taxes in some States in India [16].

Lockdowns, especially those that include statutory restrictions for people's mobility, have likely the largest potential effect on alcohol and tobacco use. Previous studies reporting the effect of COVID-19 lockdowns on alcohol use have reported a mixed picture, with some studies reporting an increase in high-risk drinking (either volume or heavy episodic drinking),[17-21] volume of alcohol use [22] and frequency of alcohol use [23], while other

studies have reported reductions in alcohol use [24-26]. Mixed changes on tobacco use have also been reported, with a relatively equal proportion of respondents describing an increase or reduction in their use of tobacco [17, 20, 27-30]. Evidence comes primarily from countries in Europe, the United States, Australia, and New Zealand. One common limitation of these studies is that they compare a pre-pandemic with a pandemic period and are thus not able to disentangle the direct effects of the pandemic with those from lockdown and curfew policies.

In this study, we will advance prior knowledge by providing evidence from a country in Latin America, one of the worst-hit regions worldwide. Latin America accounts for 8.4% of the global population, but 20.3% of the total SARS-COV2 cases and 30.2% of the COVID-19 deaths to date [31]. In addition, we will exploit the variation in lockdown policies in two regions in Chile to disentangle the effects of the COVID-19 pandemic with those from a lockdown.

The aim of the study is to examine the effect of a regional lockdown on alcohol use in two university populations in the Araucanía and Coquimbo regions in Chile. We will use a difference-in-difference analysis to obtain causal estimates of these COVID-19 policies.

Methods

Study design

The study is a controlled before-and-after study of COVID-19 policies in two Chilean regions. We will report the results in accordance with the Strengthening the Reporting of Observational Studies in Epidemiology (STROBE) statement [32].

Participants

The study population are university communities from two regions in Chile (Coquimbo, northern Chile, and Araucanía, southern Chile). These university communities include undergraduate and postgraduate students, full-time and part-time academics, leadership positions, administrative staff and service personnel. Eligibility criteria include (1) those with study rights either at the undergraduate and postgraduate levels by July 27, 2020; or (2) workers with a full-time or part-time contract with the University, including academics and assistant personnel, (3) with an email registered in the Human Resource Office of each university.

Intervention

We will examine the effect of lockdown in the context of the COVID-19 pandemic. During the study period, the Chilean Ministry of Health established a five-step process for social distancing measures. These ranged from full lockdown (step 1) to almost no restrictions (step 5). Even under full lockdown, citizens were able to obtain permits for essential activities (e.g., buying food or going to the doctor). These permits had a maximum of two per week and were obtained in a virtual station of the Chilean Police Force (Carabineros de Chile). Table S1 describes the five phases in detail. Table S2 describes the different types of permits people were allowed to use. It must be noted that, due to the COVID-19 pandemic, the Chilean government issued a night curfew with a total prohibition to leave home between 22.00 and 05.00 for the whole country from March 22, 2020, to date. Table 1 includes the specific policies implemented in both regions at the time of each data collection period.

Comparator

The comparator is the absence of lockdown at a given time. During most of the study period, the whole country had in place restrictions for public gatherings, school closures and advice for remote work. Both universities instructed remote work from March 16, 2020, which continued during the whole study period.

Covariates

We will adjust for covariates that are not influenced by the intervention but correlate with the outcome to increase the statistical power. These covariates include sex, age, educational level, living arrangements, existing medical conditions, and type of relationship with the university (i.e., student, academic or service personnel). We will categorise education into four categories: complete secondary education, incomplete undergraduate education, complete undergraduate education, and postgraduate education degree. We will categorise living arrangements into living alone or not. Existing medical conditions will be categorised into a dichotomous variable on whether the participants reported any of the following: high blood pressure; diabetes; cardiac problems (cardiac insufficiency, myocardial infarction, or others; respiratory conditions (asthma, respiratory insufficiency; depression; anxiety; other mental health problem; cancer (any malignancy including leukaemia or lymphoma; and fibromyalgia). We will categorise the type of relationship into three categories: student, service or administration personnel, and academic or leadership position.

Outcomes

We will examine three primary outcomes: weekly grams of alcohol use, heavy episodic drinking (HED) and number of cigarettes smoked per day. Weekly grams of alcohol use were measured at baseline with a question of how many drinks of beer (in portions of 330 cc), wine and similar (chicha and pipeño, two types of unfiltered wines, in portions of 140 cc) and spirits (pisco, rum, whisky, tequila, vodka, gin or other strong liquors) in a typical week. We asked the same questions for a pre-pandemic period and a during-the-pandemic period. The follow-up at waves 2 to 6 included a similar question but for each day of the week ("how many drinks did you have each day of the week").

We will convert the number of drinks into grams by multiplying the volume of each beverage by the density of alcohol (0.789). We will consider a standard drink of 15.8 grams based on the results of the Chilean National Health Survey 2009-2011, which had a standardized protocol to assess standard drinks in Chile. This data is available for all waves. Waves 0, 1, 5 and 6 include separate questions for beer, wine, and spirits.

We will measure HED with a question on how often the respondent drank 5 or more drinks on a single occasion (considering a 1-month period). The options were never, once, twice, 3 to 5 times, 6 to 9 times and 10 or more. We will convert this information into a continuous variable. We will convert the options 3-5 and 6-9 times to their arithmetic midpoint (4 and 7.5, respectively). We will convert the 10 or more option into the lower boundary (i.e., 10). This data is available for waves 0, 1, 4, 5 and 6.

We will measure the number of daily cigarettes smoked per day with a question on how many cigarettes has the participant smoked on average during the past week. We will convert this information into a continuous variable. This data is available for all waves.

Procedures

We collected the data using an online survey sent by email to all eligible participants. Data were collected from July 27 to August 13 (wave 0 and 1), August 15 to August 25 (wave 2), September 7 to September 22 (wave 3), October 5 to October 16 (wave 4), November 9 to November 20 (wave 5), December 9 to December 21 (wave 6) and April 5 to April 23 (wave 7). In all waves, we used an online survey tool (QuestionPro) which creates a database automatically. We did not allow participants to leave questions blank, but participants could stop answering at any moment. We used the following protocol to remind participants to answer the questionnaire: After sending the survey, we sent a reminder every three days: twice via email, then to those who had provided a mobile phone number, we sent the survey

two more times via text messaging. No incentive was provided in exchange for their participation in any of the study waves. The first round of data collection included questions regarding the period before the COVID-19 pandemic (wave 0) and during the pandemic (wave 1).

Sample size calculation

Prior to the beginning of the study, we calculated a sample size of 1046 participants to detect a small effect size (0.2), with a statistical power of 0.95, alpha of 0.05 and a factor of 2 to take into account the impact of attrition.

Ethical approval

The Scientific Ethics Committee from the Universidad de la Frontera and Universidad Católica del Norte approved the study in accordance with Law 20.120 (2006). We obtained electronic written consent from all participants.

Statistical analysis

We will exploit the variation in lockdown policies in the two regions to measure the effect of lockdown on alcohol use. For this purpose, we will use a difference-in-difference (DiD) design to compare the effect of lockdown in multiple treatment periods. DiD is a quasi-experimental approach that allows using longitudinal data to obtain causal effects in the absence of randomization [33]. DiD is a well-established method in public health research and was first used by John Snow in his seminal study on the transmission of cholera in 1855 [34].

The canonical DiD consists of two time periods and two groups. One computes the difference in the mean outcomes of the treatment and control group after the treatment and subtract the difference that existed before treatment had any effect [35].

$$\delta_{DD} = (\underline{Y}_{posttreat} - \underline{Y}_{pretreat}) - (\underline{Y}_{postcontrol} - \underline{Y}_{precontrol})$$

The key identifying assumption is that, in the absence of treatment, the average outcomes would have followed parallel paths over time [33].

As depicted in Figure 1, our case is more complex, as there are multiple time periods (seven in total) and two groups that are both treated and not-treated in different time periods. For τ periods and a particular time period denoted by t where $t=1,..., \tau$, t_0 represents the baseline measurement captured retrospectively at t_1 . In time periods t_1 , t_2 and t_3 , the Coquimbo group

is exposed to lockdown while the Araucanía group is exposed to less restrictive social distancing policies. At t_4 both groups are exposed to step 2 social distancing policies and at t_5 and t_6 ; this situation reverses, and Araucanía is exposed to lockdown and Coquimbo moves to less restrictive social policies. Treatment intensity *D* has values ranging from 5 (step 1) to 1 (step 5) (see Table S2 for details).

[figure not shown]

Figure 1. Social distancing policies in Coquimbo and Araucanía for the study period

In this setting, we will use a generalized difference-in-difference that allows for multiple treatment periods and several treatment intensities [36, 37]. The regression of a DiD model can be expressed in more general terms as

$$(1) Y_{ist} = \alpha + \delta_{DD} TREAT_{st} + \theta X_{ist} + \beta_i + \gamma_t + e_{ist}$$

where Y_{ist} is the outcome for an individual s at time t and i is the region (Coquimbo or Araucanía), δ_{DD} is the coefficient of interest of a treatment intensity variable, X_{ist} is a vector of control variables (e.g. age, sex), β_i is a region fixed effect, and γ_t is a set of time fixed effects. The identifying assumption, in this case, relies on a common trend assumption that both treatment groups would develop equally over time under at least one of the treatments. It assumes effect homogeneity conditional on observables X_{ist} .

An alternative to adjustment by control variables would be to use propensity score matching (PSM). Recent analyses Daw and Hartfield (2018) suggest that using PSM could increase bias due to regression to the mean when treatment assignment occurs at the population level. In this context, the difference between treatment groups is stable and unmatched analysis is unbiased. Matching on the preperiod level introduces regression to the mean bias [38]. For this reason, we chose to adjust for control variables and not to use PSM.

There is an ongoing debate about DiD when groups of units receive treatment at different times or different treatment intensities.[39, 40] Researchers are concerned this fixed effect regression provides greater weights to treatments with similar before and after treatment periods and uses treated units as controls.[39] This is unlikely to affect our study, as it has only two treated groups and thus no variation in treatment timing. Nonetheless, we will use the Callaway-Sant'Anna method (CS method) in sensitivity analyses. The method was built to handle staggered treatment adoption designs.[40] To accommodate this, we will divide the analysis into two sections (t_0 versus t_1 , t_2 and t_3) and (t_0 versus t_5 and t_6).

The estimation will be done using linear mixed effects models. These models take into account the correlated nature of the data (repeated measures of the same individuals) and provide mathematically equivalent estimates than fixed effects linear regression. However, an additional advantage of linear mixed effects models is that they allow to vary the number of observations within each participant, handling missing data more efficiently than other analytical approaches [41].

Statistical Software

We will use R (current version 3.6.3) for all analyses. We will use the *lme4* function to run the DiD model and the *did* package for the Callaway-Sant'Anna method.

References

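### Weekly grams of alcohol is asked in three different forms over the seven waves, and no planned analysis shows whether the lockdown result depends on the form

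*Combined protocol and SAP*

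**What the plan says.** Under Outcomes, the protocol states: "We will examine three primary outcomes: weekly grams of alcohol use, heavy episodic drinking (HED) and number of cigarettes smoked per day". At baseline, weekly alcohol was asked as drinks of beer, wine and spirits in a typical week. Of that item the plan says: "We asked the same questions for a pre-pandemic period and a during-the-pandemic period". These two answers are waves 0 and 1, and under Statistical analysis t_0 "represents the baseline measurement captured retrospectively at t_1". For the later waves: "The follow-up at waves 2 to 6 included a similar question but for each day of the week". A second difference follows in the same section: "Waves 0, 1, 5 and 6 include separate questions for beer, wine, and spirits".

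Read together, these give three forms:
- waves 0-1: typical week, by beverage
- waves 2-4: daily, without separate beverage questions
- waves 5-6: daily, with separate beverage questions

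All are converted to grams and treated as one outcome available at every wave. Equation (1) has covariates, one treatment coefficient and two sets of effects: "β_i is a region fixed effect, and γ_t is a set of time fixed effects". The Callaway-Sant'Anna sensitivity analysis compares t_0 with t_1 to t_3, and t_0 with t_5 and t_6. The plan has no form term, no calibration between forms, and no analysis restricted to waves with the same form.

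**The concern.** The time effects are common to both regions. They absorb a change of questionnaire if it moves both regions by the same number of grams. They do not absorb a regional difference in that movement. Such a difference would arise, for example, if the new form raised reports by a fixed percentage and the regions differed in mean intake.

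The forms are not balanced over exposure. The typical-week form covers only the baseline and Coquimbo's first lockdown wave. Araucanía's lockdown waves are the only daily waves with separate beverage questions, so the second change of form coincides with the reversal of lockdown between regions. The parallel-path assumption concerns drinking. Pooling the forms adds a further condition, that both regions respond equally to each change of form, and the plan neither states nor checks it.

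**Working it through.** The plan gives no figure on this point to reproduce. The check finds the weight with which a regional difference in form response enters each planned estimate.

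**Inputs.** D is the Coquimbo-minus-Araucanía difference in lockdown, from Statistical analysis. F marks the daily form and G the separate beverage questions, from Outcomes.

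| Wave | 0 | 1 | 2 | 3 | 4 | 5 | 6 |
|---|---|---|---|---|---|---|---|
| D (binary) | 0 | 1 | 1 | 1 | 0 | -1 | -1 |
| F | 0 | 0 | 1 | 1 | 1 | 1 | 1 |
| G | 1 | 1 | 0 | 0 | 0 | 1 | 1 |

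K1 and K2 are the regional differences (Coquimbo minus Araucanía, g/week) in the shift tied to F and to G. The documents give neither.

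**Main model, binary coding, equal wave sizes.** With region and time effects, the weight is the centred cross-product with D divided by the centred sum of squares SS.
- Mean of D = 1/7, and SS = 5 - 1/7 = 34/7 = 4.857.
- K1: sum of D×F = 0, so the cross-product is 0 - 5/7 and the weight is -5/34 = -0.147.
- K2: sum of D×G = -1, so the cross-product is -1 - 4/7 = -11/7 and the weight is -11/34 = -0.324.
- A shift equal in both regions has weight 0.

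**Unequal waves (assumed).** Sizes falling evenly to half by wave 6 give -0.125 for K1 and -0.305 for K2. Waves 0-1 at full size and waves 2-6 at half give -0.20 and -0.24.

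**Planned 5-to-1 intensity coding.** Let D = (0, a, a, a, 0, -b, -b). The less restricted region's exact steps cannot be read from the text, so steps 2 to 4 are assumed (a and b from 1 to 3). With equal waves:
- SS = 3a² + 2b² - (3a - 2b)²/7.
- The K1 cross-product is -(a + 4b)/7. The weight runs from -0.045 (a=3, b=1: -1/22) to -0.147 (a=b=1) per step, and is never zero.
- The K2 cross-product is -(5a + 6b)/7. The weight runs from -0.108 (a=b=3) to -0.324 (a=b=1) per step.

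**Simulation check.** One simulated data set with true effect 0.20, K1 = 0.3 and K2 = 0, fitted with a random-intercept model, gave 0.155 against an expected 0.156. Waves 2-6 alone gave 0.199.

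**Callaway-Sant'Anna sections, simple averaging over post periods.**
- t_0 versus t_1-t_3 (Coquimbo treated): wave 1 contributes 0, waves 2 and 3 each K1 - K2. The average is +0.67 K1 - 0.67 K2.
- t_0 versus t_5-t_6 (Araucanía treated): -1.00 K1. K2 cancels because both ends have beverage questions.
- From K1 alone, the sections differ by 1.67 K1 when the lockdown effect is the same.

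**Illustration (all assumed).** Regional means of 60 and 45 g/week and a daily form reading 20-40% higher give K1 = 15 × 0.2 to 15 × 0.4 = 3-6 g/week.
- Main model: 0.147 × 3 to 0.147 × 6 = 0.4-0.9 g/week.
- Sections: 2-4 g/week, and 3-6 g/week with the opposite sign.

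**Alternatives, binary coding, independent errors.** The SE ratio is the square root of 4.857 over the remaining SS.
- Waves 2-6 only: SS = 4, SE ratio 1.10 (1.11 and 1.18 for the two unequal-wave patterns). K1 weight 0, K2 weight -2/4 = -0.50 (-0.48 with evenly falling sizes).
- Two-level region-by-form term (waves 0-1 versus 2-6): SS = 0.5 + 4 = 4.5, SE ratio 1.04. K1 weight 0, K2 weight -2/4.5 = -0.44.
- Region-by-form terms for all three forms: SS = 0.5 + 0.667 + 0 = 1.167, SE ratio 2.04 (about 1.83 with unequal waves). Both weights are 0. Waves 5-6 contribute nothing because D is the same in both.
- Under 5-to-1 coding with equal waves, SS is 2a² + 2b² - (2a - 2b)²/5 for waves 2-6 and 7a²/6 for the three-form model. Over the assumed steps the SE ratios are 1.08-1.14 and 1.45-4.11.

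**The case against.** The strongest reply is that nothing in the documents shows K1 or K2 to be non-zero. They give no regional intake, no drinking pattern and no ratio between forms. The plan itself calls the follow-up question similar, and the proportional form effect is an assumption. This stands, and it means the point describes exposure to bias, not demonstrated bias.

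The reversal of lockdown also cancels about 85% of K1 in the main model under binary coding with equal waves. The illustrated bias of 0.4-0.9 g/week is at most 6% of one 15.8 g standard drink (0.9/15.8). This stands too. A reader might infer that the questionnaire change by itself distorts the lockdown coefficient, or distorts it materially. The documents do not support either: a shift common to both regions drops out, and no size is given for the remainder.

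A reader might also infer that waves 2-6 form a clean single-form data set, or that a two-level region-by-form term settles the matter for a 4% wider standard error. They do not. Both remove K1, but they raise the K2 weight from -0.32 to -0.50 and -0.44. Changing the main model in that way exchanges one exposure for another.

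Finally, the larger multipliers concern only a sensitivity analysis and assume simple averaging, which the plan does not state. That is correct, but it is the only sensitivity analysis planned, and both its sections use the typical-week t_0 as reference. It cannot show whether the result depends on the form.

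**Conclusion.** The point holds as a gap in the sensitivity analyses for one primary outcome. The three forms are documented, and equation (1) removes a change between them only if the regions respond equally in grams. The weights are -0.13 to -0.20 on K1 and -0.24 to -0.32 on K2 under binary coding. On K1 the weight is -0.045 to -0.147 per step under the planned coding with equal waves. The main-model bias may well be small. The Callaway-Sant'Anna sections are more exposed to K1 and can disagree with no difference in lockdown effect, which could be misread as heterogeneity or a failed check. The weights rest on the exposure pattern in the text, the assumed steps and the assumed wave sizes. The gram figures rest entirely on assumed regional means and an assumed form ratio.

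**What to change.** Keep equation (1) as the main model. State in the plan that weekly grams is measured with three forms, and add these named sensitivity analyses for that outcome:

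- **(a) Waves 2-6 only.** This removes K1 and keeps lockdown in both regions. The standard error is about 1.10-1.18 times the planned one (binary coding). State that about half of K2 remains.
- **(b) All waves with region-by-form terms for all three forms.** This removes both K1 and K2. The standard error is about 1.8-2.0 times the planned one under binary coding, and depends on the actual steps under 5-to-1 coding. State that the estimate then rests on wave 0 versus 1 and on waves 2-3 versus 4, so Araucanía's lockdown waves do not inform it.
- **(c) Callaway-Sant'Anna.** In the first section, report t_0 versus t_1 separately as the only same-form contrast, noting that t_0 is recalled at t_1. State that t_0 versus t_5-t_6 compares a typical-week form with a daily form.

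The cost is extra model runs in existing data and wider intervals in the sensitivity analyses. The main analysis and its precision do not change.

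### Between t_1 and t_6 the lockdown contrast falls with calendar time, so a regional or seasonal drift that differs between north and south would be read as a lockdown effect, and model (1) has no term to separate them

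*Combined protocol and SAP*

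**What the plan says.** Under Participants, the population comes from two regions, "Coquimbo, northern Chile, and Araucanía, southern Chile". Under Statistical analysis, at t_1 to t_3 the Coquimbo group "is exposed to lockdown while the Araucanía group is exposed to less restrictive social distancing policies". At t_4 both are at step 2. At t_5 and t_6 "Araucanía is exposed to lockdown and Coquimbo moves to less restrictive social policies". t_0 is a pre-pandemic measurement recalled at wave 1.

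Procedures gives the survey windows. The first rounds are dated "July 27 to August 13 (wave 0 and 1), August 15 to August 25 (wave 2"). The three spring rounds that follow have the dates "September 7 to September 22 (wave 3), October 5 to October 16 (wave 4), November 9 to November 20 (wave 5"). The last two are given as "December 9 to December 21 (wave 6) and April 5 to April 23 (wave 7").

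Model (1) contains a treatment-intensity term, covariates, a region fixed effect and common time effects. It rests on a common-trend assumption, and the Background says the analysis will give causal estimates. The sensitivity analysis uses the Callaway-Sant'Anna method in two sections: t_0 versus t_1 to t_3, and t_0 versus t_5 and t_6.

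The analysis states that "there are multiple time periods (seven in total"), that is, t_0 to t_6. Under Outcomes, the follow-up alcohol question is described for waves 2 to 6 and HED is available at waves 0, 1, 4, 5 and 6. For weekly grams and for cigarettes the text says "This data is available for all waves".

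**The concern.** Common wave effects remove only the seasonal change that both regions share. Suppose drinking or smoking moves differently in north and south between July and December, for example through climate or university calendars. The gap between regions then changes over the same months, and in the same order, as the lockdown gap. Model (1) has no term that separates the two, so the drift enters the lockdown coefficient. Reversing the lockdown between regions looks like protection, but it does not cancel a drift that runs in one direction from July to December.

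At stake is the causal reading of the main coefficient. No check of the common-trend assumption is planned, although the schedule offers one: at both t_0 and t_4 the two regions have the same status as each other.

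**Working it through.** **Inputs.** Wave dates come from Procedures and lockdown status from Statistical analysis. The year 2020 is inferred from the eligibility date of July 27, 2020, and 2021 for wave 7 follows from the sequence. t_0 has no date; 1 March 2020 is an assumption. Lockdown is coded 1/0. g is the lockdown gap, Coquimbo minus Araucanía. d is the wave midpoint in days from 27 July 2020.

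| | t_0 | t_1 | t_2 | t_3 | t_4 | t_5 | t_6 |
|---|---|---|---|---|---|---|---|
| g | 0 | 1 | 1 | 1 | 0 | -1 | -1 |
| d | -148 | 8.5 | 24 | 49.5 | 75.5 | 110.5 | 141 |

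The plan's count of seven periods is reproduced as t_0 to t_6. Procedures lists eight (waves 0 to 7), so wave 7 is the one not analysed.

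**Reduction.** With two regions, region and wave effects, and waves weighted equally, model (1) amounts to regressing the regional outcome gap on g across waves. A drift D in that gap gives bias b = Sgd/Sgg, where Sgd = Σ(g - mean g)(D - mean D) and Sgg = Σ(g - mean g)². Variance inflation, if a drift term is added, is 1/(1 - r²).

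**Alignment within the pandemic waves (t_1 to t_6).** For linear drift, r = -0.948. For an annual cosine peaking in mid-July (an assumed shape), r = 0.967. Intensity gaps of 1 to 3 steps in place of 1/0 leave the linear |r| at 0.93 to 0.95.

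**Bias on the planned periods, linear drift.** The drift's wave 1-to-6 span is 141 - 8.5 = 132.5 days.

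- Grams and cigarettes, t_0 to t_6: Sgg = 5 - 1/7 = 4.857. Sgd = -169.5 - 261/7 = -206.8. b = -42.6 days, and 42.6/132.5 = **0.32** of the wave 1-to-6 drift.
- HED, waves 0, 1, 4, 5, 6: Sgg = 3 - 1/5 = 2.8. Sgd = -243 + 187.5/5 = -205.5. b = -73.4 days, and 73.4/132.5 = **0.55**.
- With t_0 placed 4.5 to 12 months before 27 July 2020, the range is 0.32 to 0.27 for grams and cigarettes and 0.55 to 0.67 for HED.

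As an illustration, a drift of 0.2 SD would bias the coefficient by 0.32 × 0.2 = 0.064 SD (HED 0.55 × 0.2 = 0.11 SD). The sample size was planned to detect an effect size of 0.2.

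**Inflation if a linear region-by-time term is added, t_0 included.** r = -0.41, inflation 1.2; for HED r = -0.54, inflation 1.4. For a seasonal term, inflation is 15.4 if t_0 sits at the seasonal mean and about 3.5 if it sits at an extreme.

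**What the two Callaway-Sant'Anna sections would show.** Bias is given as a multiple of the wave 1-to-6 change in the regional gap.

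| Drift | t_0 v t_1 to t_3 | t_0 v t_5, t_6 |
|---|---|---|
| Linear from 1 March | 1.32 | -2.07 |
| Annual cosine, t_0 at its mean | 0.41 | 0.38 |

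A linear drift gives opposite signs. A seasonal cycle gives two similar estimates that appear to confirm each other.

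**What t_4 minus t_0 would show.** Under linear drift it equals (75.5 + 148)/132.5 = 1.69 times the wave 1-to-6 drift, so it is sensitive. Under the cosine with t_0 at its mean it is 0.04 times the change, so it would miss the cycle.

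**HED at wave 4.** The HED question covers one month. For answers on October 5 to 16 it reaches back to September 5 to 16, which overlaps wave 3 (September 7 to 22), when Coquimbo was locked down.

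**Adding wave 7 to model (1), t_0 included (d = 261).** Its lockdown gap is not in the readable text, so all three values are tried.

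| April gap | Sgd/Sgg | Linear bias (0.32 now) |
|---|---|---|
| +1 | -39/5.5 | 0.05 |
| 0 | -234.75/4.875 | 0.36 |
| -1 | -430.5/6 | 0.54 |

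**The case against.** The documents give no evidence that drinking or smoking follows a different seasonal path in the two regions. Both universities were remote throughout, and the plan states its common-trend assumption openly. This stands: the drift is a possibility, not a finding. It is still what the causal reading depends on, and the plan does not test it.

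The alignment also has limits. A drift that is neither monotone nor annual need not resemble the lockdown switch. Step 2 includes weekend lockdown in both regions at t_4 (Table S1), although the contrast there is still zero.

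A reader might go further in four ways that the documents do not support.

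- *That trend adjustment is impractical because inflation is 9.8 (18.8 for HED).* Those figures leave out t_0, which the plan includes. With it they are 1.2 and 1.4.
- *That nothing planned would reveal a drift.* The two Callaway-Sant'Anna sections would expose a linear one through opposite signs. They fail against a seasonal cycle.
- *That including wave 7 would break the alignment.* This depends on each region's step in April. Without a region-by-time term, linear bias rises in two of the three scenarios. With an April gap of 0, wave 7 does nothing against an annual cycle, because mid-April falls at nearly the same point of the assumed cosine as wave 4 (-0.02 against 0.07).
- *That a collected wave was dropped selectively.* The wave sets named under Outcomes end at 6, so the reference to all waves may mean waves 0 to 6. The text does not say that the outcomes were measured at wave 7.

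**Conclusion.** The point holds in a limited form. Within the pandemic waves, lockdown is largely confounded with a monotone or annual-cycle drift that differs between the regions (|r| 0.95 to 0.97), and model (1) does not remove it. Under linear drift the pooled estimate absorbs about 0.32 of the wave 1-to-6 drift, or about 0.55 for HED. The planned sensitivity analysis protects against the linear form but could falsely reassure under a seasonal one.

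The sizes assume 1/0 lockdown coding, equal weight per wave, t_0 at 1 March 2020 and the drift shapes stated. They show how much of a drift would pass into the estimate. They do not show that a drift exists. The unexplained absence of wave 7 is a gap in reporting; the documents do not show that including the wave would improve the estimate.

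**What to change.** 1. Add to Statistical analysis a sensitivity model with a region-by-calendar-time term, and a variant with a region-by-season term, using all planned periods including t_0. State the date assigned to t_0 and vary it. The linear version costs little precision on paper (inflation about 1.2, HED 1.4) but leans on a recalled, undated t_0. The seasonal version may be much less precise.
2. Report, with a confidence interval, the regional difference at t_4 minus that at t_0 as a falsification contrast for weekly grams and cigarettes. Note that it relies on recall, can be disturbed by carry-over from earlier waves, and can miss a seasonal cycle. Do not treat it as an equal-exposure contrast for HED.
3. State in advance that the coefficient will not be described as causal if the contrast differs from zero or the estimate does not survive the sensitivity models.
4. Reconcile Procedures with Outcomes and Statistical analysis on wave 7: whether each outcome was measured, each region's step in April, and why the analysis ends at t_6. Do not simply add the wave to model (1).

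The cost is a few sentences in the plan and a few runs on data already held.
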